9.5.3 Pharmacokinetic Analysis Population

The population for PK analysis includes participants in safety analysis set who had at least 1 measurable post dose plasma concentration with an adequately documented dosing history.

9.6 Statistical Methods

9.6.1 Statistical Methods for Efficacy Analyses

This section describes the statistical methods that address the primary and secondary efficacy objectives. Methods related to exploratory objectives will be described in the sSAP.

Antitumor activity data will be analyzed by each tumor type. The data cutoff for the primary study analysis for a given tumor type will be determined by the study team, based on the review of data at each interim analysis and predetermined futility guidance.

Only those participants who have measurable disease present at baseline and have their disease re-evaluated at postbaseline visits will be considered evaluable for ORR. These participants will have their response classified according to RECIST 1.1 or RANO for participants with HGG.

Primary Efficacy Analysis

ORR: Objective responses will count only confirmed CR and PR at Week 16. Estimated ORR and its exact 95% CI using the method of Clopper and Pearson will be presented.

Secondary Efficacy Analyses

The BOR will be provided with the descriptive statistics. The ORR, DCR, and CBR will be provided with exact 95% CIs using the method of Clopper and Pearson, and the DOR will be analyzed for responders using Kaplan-Meier approach.

The secondary endpoint of PFS will be analyzed using Kaplan-Meier product-limit estimates. Median PFS and the cumulative probability of PFS at 4, 6, 12, and 24 months will be presented with 2-sided, 95% CIs when an adequate number of at-risk participants at those time points warrant the estimate. The cumulative PFS probabilities will be plotted over time as appropriate.

A summary of the primary analysis strategy for the key efficacy endpoints is provided in [Table 5](#).

Table 5 Table Analysis Strategy for Key Efficacy Variables

Endpoint/Variable	Statistical Method	Analysis Population	Missing Data Approach
Primary Analyses – Within tumor type			
ORR (RECIST 1.1 or RANO for HGG) at Week 16	Summary statistics using Clopper and Pearson method	EAS	Participants in EAS with missing data are considered nonresponders.
Secondary Analyses – Within tumor type			
ORR	Summary statistics using Clopper and Pearson method	EAS	Participants in EAS with missing data are considered nonresponders.
BOR	Summary statistics using Clopper and Pearson method	EAS	Missing observation in EAS population are counted as nonresponders.
DCR	Summary statistics using Clopper and Pearson method	EAS	Missing observation in EAS population are counted as nonresponders.
CBR	Summary statistics using Clopper and Pearson method	EAS	Missing observation in EAS population are counted as nonresponders.
DOR	Summary statistics using Kaplan-Meier method	All responders in EAS	Nonresponders are excluded in analysis.
PFS (RECIST 1.1 or RANO for HGG)	Summary statistics using Kaplan-Meier method	EAS	Censored at last assessment.
Abbreviations: BOR=best overall response; CBR=clinical benefit rate; DCR = disease control rate; DOR = duration of response; EAS = evaluable analysis set; ORR=overall response rate; PFS = progression-free survival; RANO= Response Assessment in Neuro-Oncology; RECIST 1.1 = Response Evaluation Criteria in Solid Tumors Version 1.1.			

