4 STUDY DESIGN

4.1 Overall Design

This is an open-label, multicenter, Phase 2 basket study to evaluate the antitumor activity and safety of lenvatinib in children, adolescents, and young adults between 2 to ≤ 21 years of age with relapsed or refractory malignant solid tumors. Four cohorts will be evaluated: HGG, RMS, EWS/pPNET, and any other solid tumors (aside from osteosarcoma).

A minimum of 36 participants will be enrolled, 9 evaluable participants in each of 4 cohorts: HGG, RMS, EWS/pPNET, and other solid tumors, as follows:

- HGG: at least 9 evaluable participants (a minimum of 6 participants <17 years of age)
- RMS: at least 9 evaluable participants (a minimum of 6 participants <17 years of age)
- EWS/pPNET: at least 9 evaluable participants (a minimum of 6 participants <17 years of age)
- Other solid tumor types: at least 9 evaluable participants (with any number of pediatric participants across all other tumor types).

The final sample size of patients will depend on the number of tumor types that meet the futility bar and the antitumor activity observed in evaluable participants in the corresponding tumor cohort in Study E7080-A001-216. The enrollment in the HGG, RMS, and EWS/pPNET cohorts is capped at a maximum of 17 evaluable participants each. The enrollment for each tumor type expanded based on response in the other solid tumors' cohort is also capped at a maximum of 17 evaluable participants. Based on these factors and the projected enrollment period, it is estimated that up to approximately 150 participants could be enrolled. Participants will meet the criteria for being evaluable for an objective response if they have measurable disease present at baseline and at least 1 postbaseline efficacy assessment, unless they have discontinued prior to the first efficacy assessment due to progressive disease. Participants who are not evaluable for objective response will be replaced.

Expansion portion of the study: This study uses a sequential monitoring procedure to evaluate for futility and to evaluate efficacy of lenvatinib by assessing antitumor activity. IAs will be performed after 9 evaluable participants are enrolled in each of the 3 target tumor

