5.5 Participant Replacement Strategy

A participant who is not evaluable for objective response will be replaced.

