6.5.1 Prohibited Concomitant Medications

Participants are prohibited from receiving the following therapies during screening and while on treatment during the study:

- Concurrent anticancer therapies such as chemotherapy, TKIs, radiotherapy (with the exception of palliative radiotherapy as specified in Section 6.5), antitumor interventions (surgical resection, surgical debulking of tumor, etc.), or cancer immunotherapy.
- Concurrent other investigational drugs.

For participants who, in the assessment by the investigator, require the use of any of the aforementioned treatments for clinical management, continuation of the study medication, and further participation in the study must be discussed and agreed upon with the Sponsor.

If participants receive additional anticancer therapies, this will be judged to represent evidence of disease progression, and study medication will be discontinued. These participants should complete all off-treatment assessments and continue to be followed for survival in the Survival Follow-up Period.

Further information on the prohibited concomitant therapies for lenvatinib is included in the prescribing information.

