9.1 Statistical Analysis Plan Summary

Key elements of the SAP are summarized below; the comprehensive plan is provided in Sections 9.1-9.12.

Study Design Overview	An Open-Label, Multicenter Phase 2 Basket Study to Evaluate the antitumor activity and Safety of Lenvatinib in Children, Adolescents, and Young Adults with Relapsed or Refractory Solid Malignancies
Treatment Assignment	
A minimum of 36 evaluable participants will be enrolled: 9 evaluable participants in each of the tumor types. The final sample size of participants will depend on the number of tumor types that meet the futility bar and the antitumor activity in evaluable participants observed in the corresponding tumor cohort in Study E7080-A001-216. The enrollment in the HGG, RMS, and EWS/pPNET cohorts is capped at a maximum of 17 evaluable participants each. The enrollment for each tumor type expanded based on response in the other solid tumors' cohort is also capped at a maximum of 17 evaluable participants. Based on these factors and the projected enrollment period, it is estimated that up to approximately 150 participants could be enrolled.
 
The participants will receive lenvatinib 14 mg/m² orally once daily (equivalent to 24 mg QD, the adult daily dose).

Analysis Populations	
Antitumor activity: Evaluable Analysis Set (EAS), defined as all evaluable participants, who have measurable disease present at baseline and at least 1 postbaseline efficacy assessment, unless they have discontinued prior to the first efficacy assessment due to progressive disease.
 
Safety: Safety Analysis Set, defined as all participants who received at least 1 dose of the study drug.
 
Pharmacokinetic (PK): PK Analysis Set, defined as participants in Safety Analysis Set who had at least 1 measurable postdose plasma concentration with an adequately documented dosing history.

Primary Endpoint(s)	
The Primary Endpoint will be assessed for each tumor type: ORR, defined as the proportion of participants with a confirmed (≥ 4 weeks after initial response) CR or PR per RECIST 1.1 or RANO for HGG as assessed by investigator, at Week 16.

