9.5 Analysis Populations

9.5.1 Efficacy Analysis Population

The EAS population will serve as the primary population for the analysis of antitumor activity data within each tumor type in this study. EAS is defined as all evaluable participants, who have measurable disease present at baseline and at least 1 postbaseline efficacy assessment, unless they have discontinued prior to the first efficacy assessment due to progressive disease. Details on the approach to handling missing data are provided in [Table 5](#).

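### Section 9.6.1 drops the early-progression exception from the ORR denominator, against the EAS and Table 5; unscanned non-PD leavers are replaced, with no all-treated ORR in the visible text

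*Combined protocol and SAP*

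**What the plan says.** Section 9.5.1 names the EAS as the primary population for antitumour activity. It requires measurable disease at baseline and "at least 1 postbaseline efficacy assessment, unless they have discontinued prior to the first efficacy assessment due to progressive disease". Sections 1.1 and 4.1 and the summary in Section 9.1 give the same rule; Section 9.1 repeats the exception as "unless they have discontinued prior to the first efficacy assessment due to progressive disease".

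The methods text in Section 9.6.1 is narrower: "Only those participants who have measurable disease present at baseline and have their disease re-evaluated at postbaseline visits will be considered evaluable for ORR". It contains no exception for early progression. Table 5, later in the same section, gives the EAS as the population for Week 16 ORR, with the rule "Participants in EAS with missing data are considered nonresponders".

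On replacement, Section 4.1 says "Participants who are not evaluable for objective response will be replaced", and Section 5.5 says "A participant who is not evaluable for objective response will be replaced". The all-treated set in Section 9.5.2 is assigned to safety only. Table 5 also analyses PFS in the EAS, with the missing-data rule "Censored at last assessment".

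**The concern.** Week 16 ORR per tumour type is the primary endpoint, and two rules for its denominator stand side by side. They disagree about participants who stop for progression before any postbaseline assessment. Those participants are certain non-responders: the EAS counts them, while the Section 9.6.1 sentence leaves them out.

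A second group is missed whichever rule is used. These are treated participants with no postbaseline assessment who leave for a reason other than progression, mainly by withdrawing consent, being lost to follow-up, or dying early without the death being classed as progression. They are outside the EAS, so the nonresponder rule in Table 5 does not reach them, and they are replaced.

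In a single-arm, open-label study with an investigator-assessed endpoint and 9 to 17 evaluable participants per cohort, each such participant is a visible part of the denominator. A reader should be able to see how many were treated and then replaced.

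**Working it through.** **Side by side.** For a participant with measurable disease at baseline:

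| Situation | EAS (1.1, 4.1, 9.1, 9.5.1; Table 5) | Section 9.6.1 sentence |
|---|---|---|
| Assessed postbaseline | in | in |
| No assessment, stopped for PD | in, non-responder | out, replaced |
| No assessment, left for another reason | out, replaced | out, replaced |

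The second row is the contradiction. The third row is the gap on which both rules agree. Section 4.4 sides with the EAS, because its futility wording counts PD discontinuations before Week 16 among the first 9.

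**Direction.** A response must be confirmed on imaging, so a participant who is never re-evaluated cannot be a responder. Let x be the responders, n the participants analysed and k those excluded and replaced. The reported rate is x/n and the rate with everyone counted is x/(n + k). The ratio of reported to full rate is (n + k)/n, which exceeds 1 whenever x and k are above 0. With x = 0 both rates are 0%.

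**Check of the interval routine.** The trial's own sample-size and interim figures are redacted, so there is no figure of its own to reproduce. The background osteosarcoma cohort in Section 2.2.1.2 reports 2 responders among 30 with measurable disease as 6.7% (0.8, 22.1). Clopper-Pearson on 2/30 gives 6.7% (0.8, 22.1), which matches.

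**Size.** The maximum n = 17 and minimum n = 9 come from Section 4.1. The values of x and k are assumptions, because the documents do not give them. Intervals are Clopper-Pearson 95%, as in Section 9.6.1.

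| x | n + k | Rate (95% CI) | (n + k)/n |
|---|---|---|---|
| 4 | 17 (reported) | 23.5% (6.8 to 49.9) | 1 |
| 4 | 18 | 22.2% (6.4 to 47.6) | 18/17 = 1.06 |
| 4 | 19 | 21.1% (6.1 to 45.6) | 19/17 = 1.12 |
| 4 | 20 | 20.0% (5.7 to 43.7) | 20/17 = 1.18 |
| 1 | 9 (reported) | 11.1% (0.3 to 48.2) | 1 |
| 1 | 10 | 10.0% (0.3 to 44.5) | 10/9 = 1.11 |
| 1 | 11 | 9.1% (0.2 to 41.3) | 11/9 = 1.22 |

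The largest shift shown is 23.5 − 20.0 = 3.5 points, beside an interval 49.9 − 6.8 = 43.1 points wide.

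**PFS.** Section 9.4.1 makes death a PFS event. A death before any assessment that is not classed as progression falls outside the EAS, so the analysis omits that event. An unscanned survivor censored at day 1 would not move the curve. No percentage is given, because one would need assumptions about censoring.

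**The case against.** The strongest reply is that the Section 9.6.1 sentence is a drafting slip with an obvious answer. Four sections carry the exception, Section 4.4 agrees with them, and Table 5 names the EAS. The affected group is also small: Section 7.1 ties stopping for progression to RECIST 1.1 or RANO, so most such participants will have been re-evaluated. This stands as to intent and size. It does not remove the conflict, because the sentence sits in the methods section for the primary endpoint and its wording admits no exception.

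On the second group, an evaluable set with replacement is declared openly and in advance, and the plan narrows the group. Section 8.2.1.3 expects an end-of-treatment scan and continued imaging after stopping without progression. Section 6.5.1 adds: "If participants receive additional anticancer therapies, this will be judged to represent evidence of disease progression, and study medication will be discontinued". Section 9.6.3 will show the number allocated and the reasons for discontinuation, from which a reader could approximate an all-treated rate. All of this is fair. But imaging ends with consent withdrawal or death, and Section 9.6.3 does not clearly promise disposition by tumour type or a count of replaced participants.

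Three stronger readings are tempting and are not supported:

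- A reader might infer that no all-treated ORR is planned anywhere. The supplemental SAP is not supplied, so only the visible text can be judged. Sections 9.5 and 9.6.1, where such an analysis would naturally appear, are not redacted and contain none.
- A reader might infer that many participants go unscanned because Section 8.2.1.3 waives the end-of-treatment scan when imaging is recent. Since scheduled imaging continues after stopping, the waiver mostly defers assessment and does not size the group.
- A reader might infer that the stopping rule of 0 responses in 9 is weakened. Section 4.4 counts early progression there, and the interim section is redacted.

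**Conclusion.** The Section 9.6.1 sentence is wrong as written. It contradicts the EAS definition and the table in its own section and, taken literally, biases the primary ORR upward or leaves it unchanged. The lack of a supportive all-treated ORR is a separate, smaller gap, asserted for the visible text only.

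The likely numerical effect is modest: about 1 to 3.5 points in the scenarios shown, well inside the confidence intervals, and nothing where there are no responders. That rests on assumed counts of 1 to 3 excluded participants. The 17-participant case is the cap and not an observed size: the EWS and HGG cohorts were not expanded, enrolment to the other-tumours cohort was discontinued, and the documents do not say that RMS reached 17. The case for change is that the primary denominator should follow one rule and that replaced participants should be visible. It is not that a conclusion would reverse. The PFS consequence concerns a secondary, descriptive endpoint and is minor.

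**What to change.** (a) In Section 9.6.1, replace the sentence on who is evaluable for ORR with a reference to the EAS as defined in Section 9.5.1, early-progression exception included.

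(b) Keep the EAS as the primary population. Add, per tumour type, a supportive Week 16 ORR with its Clopper-Pearson interval in all treated participants with measurable disease at baseline, counting no postbaseline assessment as non-response. Beside it, give the number of replaced participants and the reason for each.

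(c) Optionally, add a supportive PFS analysis in all treated participants in which every death is an event.

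The cost is one corrected sentence and one extra table per tumour type, from data already collected. The supportive ORR may come out slightly lower than the EAS figure.

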	
Participants who discontinue lenvatinib treatment for reasons other than radiographic disease progression or initiation of new anticancer therapy will have post-treatment follow-up imaging for disease status every 8 weeks for up to 24 weeks, then every 12 weeks thereafter until documentation of disease progression or start of a new anticancer agent, whichever occurs first, unless the participant withdraws consent, becomes lost to follow-up, or the study is terminated. Participants who discontinue lenvatinib treatment due to documented radiographic disease progression or initiation of new anticancer therapy will move to survival follow-up.
 
Participants will be followed by telephone every 12 weeks for survival status until death unless the participant withdraws consent, becomes lost to follow-up, or the study is terminated.
 
A database lock for the primary analysis will occur when all participants in all cohorts have discontinued the study or if the last evaluable participant has completed the Week 16 imaging assessment, whichever comes first.
 
Enrollment will be stopped for a specific cohort/tumor type if no objective responses occur in the first 9 evaluable participants (i.e., the futility boundary is crossed), or a lack of antitumor activity is concluded for the corresponding tumor cohort in Study E7080-A001-216.
 
EWS and HGG cohorts were not expanded because futility was concluded for the corresponding cohorts in Study E7080-A001-216. Further enrollment of participants into the other solid tumors' cohort was discontinued due to insufficient antitumor activity of lenvatinib in this patient population.
 
The overall study ends when the last evaluable participant completes the last study-related telephone call or visit, withdraws consent, or is lost to follow-up (ie, the participant is unable to be contacted by the investigator).
 
Additional details are in Section 4.1.

--	---

Study Governance Committees:

Steering Committee	No
Executive Oversight Committee	No
Data Monitoring Committee	Yes
Clinical Adjudication Committee	No
Study governance considerations are outlined in Appendix 1.	

[figure not shown]
Study Accepts Healthy Volunteers: No

A list of abbreviations used in this document can be found in Appendix 15.

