8.2.1.2 Tumor Imaging During the Study

The first on-study imaging assessment should be performed the end of Week 8 \pm 7 days. Subsequent tumor imaging should be performed every 8 weeks until Week 24, then every 12 weeks (\pm 7days) thereafter during treatment (or sooner if there is evidence of PD). Imaging timing should follow calendar days from C1D1, and should not be adjusted for delays in cycle starts. Imaging should continue to be performed until disease progression is identified by the investigator, the start of new anticancer treatment, pregnancy, withdrawal of consent, or death, whichever occurs first.

Objective response should be confirmed by a repeat imaging assessment. Tumor imaging to confirm PR or CR should be performed at least 4 weeks after the first indication of a response is observed. Participants will then return to regular scheduled imaging, starting with the next scheduled imaging time point. Participants who receive additional imaging for confirmation do not need to undergo the next scheduled tumor imaging if it is less than 4 weeks later; tumor imaging may resume at the subsequent scheduled imaging time point.

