8.2.1.4 RECIST 1.1 Assessment of Disease

RECIST 1.1 will be used as the primary measure for assessment of tumor response (except for HGG), for date of disease progression, and as a basis for all protocol guidelines related to disease status (eg, discontinuation of study intervention). RECIST 1.1 references a maximum of 5 target lesions in total and 2 per organ.

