8.11.5.2 Efficacy Follow-up Visits

Participants who discontinue lenvatinib for a reason other than disease progression and/or initiation of new anticancer therapy will move into the Efficacy Follow-up Phase and will be assessed as outlined in the SoA (Section 1.3) to monitor disease status. Every effort should be made to collect information regarding disease status until the start of new anticancer therapy, disease progression, death, end of study, whichever occurs first. Information regarding poststudy anticancer treatment will be collected if new treatment is initiated. Participants who completed all efficacy assessments and/or will not have further efficacy assessments must enter the Survival Follow-up Phase.

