9.4.1 Efficacy Endpoints

Primary Endpoints

- **ORR:** defined as the proportion of participants with a confirmed (≥ 4 weeks after initial response) CR or PR per RECIST 1.1 or RANO for HGG as assessed by investigator, at Week 16.

Secondary Endpoints

- **ORR.**
- **BOR:** defined as the participant's best confirmed response (CR or PR) over the treatment period.
- **DOR:** defined as the time from the date of the first documented CR or PR to the date of the disease progression objectively documented or death (whichever occurs first).
- **DCR:** defined as the percentage of participants who have a BOR of CR, PR, or SD. To be assigned a best overall response of SD, the time from the first administration of study drug until the date of documented SD should be ≥ 7 weeks.
- **CBR:** defined as the percentage of participants who have a BOR of CR, PR, or durable SD (SD duration ≥ 23 weeks since the first dose of the study treatment).
- **PFS:** defined as the time from the date of the first administration of study drug until the date of first documentation of PD per RECIST 1.1 or RANO for HGG or death (whichever occurs first).

Tertiary/Exploratory Endpoints

- **OS:** defined as the time from the date of the first administration of study drug until the date of death from any cause.

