Steroid dose is defined as the average daily dose since last visit. A dose of "none" means no corticosteroids above physiologic replacement dose. The dose is considered "stable" if it is unchanged or decreased from the visit at which the scans showed the smallest tumor burden. The dose is considered "increased" if it has increased from the visit at which the scans showed the smallest tumor burden.

For any overall response except PD, all the components of the definition (radiological, neurological, and steroid dose) must be present. However, either radiological progression or clinical deterioration (not attributable to a non-tumor-related cause) qualifies a participant for PD. However, an increase in steroid dose alone is not sufficient for an overall visit response of PD in the absence of clinical or radiological evidence of progression. A participant with a radiological response of SD, and without neurological evidence of progression, but requiring an increased dose of steroids, would still be considered SD overall at that visit (because increase in steroids alone is not PD). However, the participant will be reassessed at the next visit. If either radiological or neurological progression is documented at that next visit, the visit at which the increased dose was first observed would be retroactively reassessed as PD overall.

Table 11 Overall Response

Radiographic Response	Clinical Performance	Steroid Dose	Overall Response
CR	Stable	None	CR
CR	Stable	Stable or increased	PR
PR	Stable	Stable	PR
PR	Stable	Increased	SD
SD	Stable	Stable	SD
SD	Stable	Increased	SD or PD ^a
PD	Any	Any	PD
Any	Worsening	Any	PD
NE	Stable	Increased	NE or PD ^a
NED	Stable	Increased	NED or PD ^a

^a PD should not be based on an increase in steroid dose alone, unless confirmed by radiographic or clinical deterioration. If the steroid dose is increased while the radiographic assessment and clinical performance are stable, the participant should be re-evaluated at the next visit. If clinical or radiographic deterioration has occurred, progression can be retrospectively assigned at the visit when the steroid dose was increased.

Pseudoresponse and response confirmation

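### In the RECIST cohorts, a participant who stops for progression before any postbaseline scan stays in the PFS population, but Section 9 can censor that progression instead of counting it, which can inflate PFS

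*Combined protocol and SAP*

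**What the plan says.** - **Population.** Sections 9.1 and 9.5.1 define the EAS as participants with measurable disease at baseline and a postbaseline efficacy assessment, "unless they have discontinued prior to the first efficacy assessment due to progressive disease". Table 5 (Section 9.6.1) names the EAS as the PFS population.
- **Event.** Section 9.4.1 runs PFS from first dose "until the date of first documentation of PD per RECIST 1.1 or RANO for HGG or death (whichever occurs first"). Section 8.2.1.4 adds that "RECIST 1.1 will be used as the primary measure for assessment of tumor response (except for HGG), for date of disease progression".
- **Censoring.** The missing-data entry for PFS in Table 5 is "Censored at last assessment". No date is given for a participant with no assessment after baseline.
- **HGG.** Under RANO (Appendix 8), "either radiological progression or clinical deterioration (not attributable to a non-tumor-related cause) qualifies a participant for PD".
- **Scan timing.** "The first on-study imaging assessment should be performed the end of Week 8" (±7 days), or earlier on evidence of progression (Section 8.2.1.2). Section 8.2.1.3 expects a scan at treatment discontinuation (±4 weeks), but waives it if imaging was done in the preceding 4 weeks.
- **Imaging after stopping.** The Synopsis says "Participants who discontinue lenvatinib treatment for reasons other than radiographic disease progression or initiation of new anticancer therapy will have post-treatment follow-up imaging"; Section 4.1 agrees. Section 8.2.1.3 continues imaging when progression has not been documented. Section 8.11.5.2 says "Participants who discontinue lenvatinib for a reason other than disease progression and/or initiation of new anticancer therapy will move into the Efficacy Follow-up Phase", without the qualifier.

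**The concern.** The same early stop is accepted as progression when deciding who is evaluable, and counts as a nonresponse for ORR. For PFS it has neither an event rule nor a date. If no scan follows, the participant leaves the risk set because the disease progressed. Kaplan-Meier estimation assumes that censored participants have the same prognosis as those still at risk, and here that is plainly false.

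PFS is a key secondary endpoint. Median PFS and PFS rates at 4, 6, 12 and 24 months are planned for each tumor type, in groups capped at 17 evaluable participants and possibly as small as 9. One or two such participants can move the estimate. The rule cannot simply be left to the supplemental SAP, because Section 9.6.1 says that it covers the primary and secondary efficacy methods and defers only exploratory ones.

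**Working it through.** The documents give no PFS event count or power figure to reproduce (Sections 9.7.2 and 9.9 are blacked out and are not treated as gaps). The check has three parts.

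**1. What the rules do to one participant in a RECIST cohort**

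A participant stops before Week 8 for progression judged clinically, without a scan.

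- EAS: included through the exception in Section 9.5.1.
- PFS event: none, because there is no RECIST progression.
- Censoring date: the only assessment is the screening scan, taken up to 28 days before allocation (Section 8.2.1.1), whereas PFS time starts at first dose. The last assessment can therefore precede time 0. Setting the date to Day 1 is the natural default, but that is an inference.
- Later death: an event, dated at death.
- Later scan showing progression: an event, dated at that scan.

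**2. Whether a later scan is assured**

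- A screening scan taken d days before first dose satisfies the 4-week waiver for any stop within 28 − d days of first dose. With d = 14, that covers stops in the first 14 days.
- After a clinical stop, the Synopsis, Section 4.1 and Section 8.2.1.3 continue imaging. Section 8.11.5.2, read literally, does not.
- Follow-up imaging ends when new anticancer therapy starts. Section 6.5.1 treats additional anticancer therapy as evidence of progression, but Section 9 does not carry this into PFS.

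A later scan is therefore likely, but not guaranteed.

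**3. Size if some are never scanned**

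Let k of n participants be such cases, with no other censoring before time t. Censored at time 0, the curve is that of the other n − k. Counted as events before t, it is that curve times (n − k)/n. The ratio is n/(n − k). The sizes 9 and 17 come from Section 4.1. The values of k, and a 4-month PFS of 1/3 among the rest, are assumptions.

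| n | k | n/(n−k) | Censored at time 0 | Counted as early events |
|---|---|---|---|---|
| 17 | 1 | 17/16 = 1.06 | 33.3% | 33.3% × 16/17 = 31.4% |
| 17 | 2 | 17/15 = 1.13 | 33.3% | 33.3% × 15/17 = 29.4% |
| 17 | 3 | 17/14 = 1.21 | 33.3% | 33.3% × 14/17 = 27.5% |
| 9 | 1 | 9/8 = 1.13 | 33.3% | 33.3% × 8/9 = 29.6% |
| 9 | 2 | 9/7 = 1.29 | 33.3% | 33.3% × 7/9 = 25.9% |
| 9 | 3 | 9/6 = 1.50 | 33.3% | 33.3% × 6/9 = 22.2% |

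A simulation links k to a rate: n = 17, exponential PFS, scans at Weeks 8, 16 and 24 and then every 12 weeks, and 10%, 25% or 50% of pre-Week-8 progressors unscanned (assumed).

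- **Median 3.0 months** (the Study 207 osteosarcoma figure in Section 2.2.1.2, borrowed as an assumption). Mean k is about 0.6, 1.5 and 3.0. Time-0 censoring raises 4-month PFS from about 43% to 44%, 47% and 52%. The typical sample median stays at Week 16.
- **Median 1.8 months** (lower confidence limit of that figure). 4-month PFS rises from about 24–25% to 26%, 28% and 34%, and the typical sample median moves from Week 8 to Week 16.
- **Event 30 days late instead of censoring.** 4-month PFS does not change: the latest possible date is 56 + 30 = 86 days, before 4 months (about 122 days).
- **Event 90 days late.** With the 3.0-month median, 4-month PFS rises from about 43% to 44%, 46% and 49%.

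**The case against.** The strongest case against is that this is only a missing date, for people who will rarely exist.

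- **HGG is covered.** A reader might infer that the gap affects every cohort. It does not: Section 9.4.1 uses RANO for HGG, and RANO makes tumor-related clinical deterioration a progression event. This stands, and limits the point to the RECIST cohorts.
- **Scans will usually follow.** Section 8.2.1.3 expects a discontinuation scan and continued imaging without documented progression. Section 8.2.1.4 makes RECIST the basis for disease-status guidelines, so progression in Section 8.11.5.2 may itself mean RECIST progression. This largely stands: the usual result may be an event some weeks late. It does not cover the waiver, an early switch of therapy, or a site that reads Section 8.11.5.2 literally.
- **The exception need not mean clinical progression only.** It could also cover an unscheduled scan before Week 8, or an early death. Those cases are proper PFS events, and the gap concerns only the remainder. Section 7.1 lists lack of clinical benefit apart from objective progression, so some clinical stops may be recorded there. The exception would then not apply, and a participant without a postbaseline assessment would leave the EAS and be replaced, so the progression would still go uncounted.
- **The shift is small against the noise.** With 5 of 17 progression-free, the exact 95% interval is 10.3% to 56.0%. True, but the interval reflects chance, whereas this error runs in one direction.
- **PFS drives no decision.** The futility rule uses ORR, and no PFS test is described. This stands and limits the consequence.

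**Conclusion.** The point holds for the RMS, EWS/pPNET and other solid tumors cohorts. Section 9 admits progression without a scan into the PFS population, but supplies no event or date for it. Applied as written, the rule censors an unscanned clinical progressor because of progression, or waits for a death. The bias is upward: a factor of 1.06 to 1.21 at n = 17 and 1.13 to 1.50 at n = 9 for one to three participants censored at time 0.

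Those factors rest on an assumed k, on an inferred Day 1 censoring date, and on these participants having neither a scan showing progression nor an observed death before the time point. A reader might infer that the reported PFS will be overstated. The documents do not support that: nothing shows how many participants lack a later scan, and with a 30-day delay the 4-month rate does not move. PFS can be inflated; whether it is depends on conduct. The primary ORR is not affected by this rule. The change should be made because it is cheap and the direction of error is known.

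**What to change.** 1. Keep RECIST/RANO PFS as the main analysis. Making investigator-judged progression the main event is a debatable trade-off and is not needed here.
2. In Table 5, state the date used when an EAS participant has no postbaseline assessment and no event.
3. Add a PFS sensitivity analysis that counts discontinuation for progression before the first postbaseline assessment as an event on the recorded progression or discontinuation date. Report the number of such participants by tumor type.
4. Reconcile Section 8.11.5.2 with the Synopsis and Sections 4.1 and 8.2.1.3, so that participants without documented RECIST or RANO progression stay in imaging follow-up. State in Section 9 how new anticancer therapy (Section 6.5.1) is handled for PFS.

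The cost is wording in the protocol and Section 9, one extra table, and a slightly less favourable PFS figure in the sensitivity analysis.
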